to Hong Kong Chinese, with high attendance rate (92%) and low attrition rate (13%). Cultural issues identified in the pilot have been published and recommendations were made in adapting the protocol to the Hong Kong cultural settings (Wong et al., 2017). A Hong Kong Chinese version of the manual for CST group leaders has been published in 2017 (Spector, Thorgrimsen, Woods, & Orrell, 2017).

This healthcare promotion project aims to enhance the quality of life and cognition of people with mild-to-moderate cognitive impairment through the use of CST-HK delivered by trained non-professional group leaders. As part of project evaluation, we aim to test the effectiveness of CST-HK compared with a wait-list control group who will receive care as usual during the waiting period.

Research Objectives

The research aims to investigate the effectiveness of CST-HK among people with mild-tomoderate cognitive impairment in Hong Kong in a larger scale across service settings. We also aim to explore the effectiveness of CST-HK delivered by non-professional staff, as a possible solution to address the shortage of specialized healthcare manpower and increasing demands of non-pharmacological interventions for people with dementia.

Hypotheses

We hypothesized that, compared with the wait-list control group, the group who have received a 7-week (14-session) CST-HK intervention delivered by trained non-professional staff will show greater improvement or maintenance of (1) quality of life; and (2) cognitive performance.

Research Design

This is a cluster randomized wait-list control study.

Study Sample

A total of 128 older persons with mild to moderate cognitive impairment will be recruited from nine service units of Hong Kong Young Women's Christian Association, including two residential care units and seven community care units. This sample size is calculated based on the primary outcomes of quality of life and cognitive function. Repeated measure analysis of variance (ANOVA), between factors will be used. Assuming a medium effect size (f = 0.25), 80% power and 5% significance level, with two groups and two time points (calculated using G*Power 3.1.9.2), a total of 98 participants are required. We propose a sample size of 128 to accommodate for a 30% attrition rate.

Inclusion and exclusion criteria are:

- A clinical diagnosis of mild-to-moderate dementia, or a cognitive assessment result suggestive of mild-to-moderate cognitive impairment;

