The person with dementia and their caregivers will undergo an interview at study baseline and 7 weeks. A service assistant blind to the group allocation will conduct the interviews. The interview will last for approximately 45 minutes for the person with dementia and the caregiver, respectively. A post-intervention assessment will be conducted in the wait-list control group upon completion of the delayed intervention.

Measurements for Primary Outcomes

The primary outcome of CST-HK, quality of life, will be measured using the Quality of Life in Alzheimer's Disease scale (Chan, Chu, Lee, Li, & Yu, 2011; Logsdon, Gibbons, McCurry, & Teri, 2002). Self-rating of the persons with dementia would be used in this study using the patient version of this tool.

Cognitive function will be measured using the Alzheimer's Disease Assessment Scale-Cognitive Subscale test (Chu et al., 2000). No deterioration in cognition is defined as a change in the score of ≥ 0 point in ADAS-Cog, and clinically meaningful improvement a change in score of ≥ 4 points, in the post-intervention assessment compared with baseline score.

Data Analysis

Intention-to-treat analysis will be conducted. For the main outcome measures of quality of life and cognition, ANOVA will be used to assess changes from baseline to 7 weeks after between the intervention group and the wait-list control group. Further analysis will be conducted by ANCOVA controlling for baseline differences in age, gender, education level, type of care setting, AChEI use (using random effects) and baseline cognition and quality of life. As a sensitivity analysis, we will also conduct exploratory analysis including the post-intervention data from the wait-list control group.

References

- Chan, I. W. P., Chu, L. W., Lee, P. W., Li, S. W., & Yu, K. K. (2011). Effects of cognitive function and depressive mood on the quality of life in Chinese Alzheimer's disease patients in Hong Kong. *Geriatrics & gerontology international*, 11(1), 69-76.

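### The lead analysis is an unadjusted ANOVA of change that by default uses only participants with both scores; the baseline-adjusted analysis already planned should be primary, with a missing-data sensitivity analysis

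*Combined protocol and SAP*

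**What the plan says.** The Data Analysis section opens with "Intention-to-treat analysis will be conducted" and does not define the analysis set. One lead method is then set for both main outcomes: "ANOVA will be used to assess changes from baseline to 7 weeks after between the intervention group and the wait-list control group". An ANCOVA that includes baseline cognition and quality of life among its covariates follows as further analysis. The only sensitivity analysis named adds the wait-list arm's scores from after its delayed programme.

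Under Intervention and Procedures, participants "will undergo an interview at study baseline and 7 weeks", so the between-arm comparison has one post-baseline score per person. Under Study Sample, the sizing rests on this method: "Repeated measure analysis of variance (ANOVA), between factors will be used". The total is then raised for losses: "We propose a sample size of 128 to accommodate for a 30% attrition rate". The Background reports 13% attrition in the Hong Kong pilot.

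The document gives no imputation rule, no missing-data assumption, no sensitivity analysis for missing 7-week scores, and no statement on assessing people who stop attending.

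**The concern.** A person without a 7-week score has no change score, so the named method leaves that person out unless something further is specified. Enlarging the sample for attrition restores power. It does nothing about who is missing.

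An unadjusted change score has a further weakness. Change is usually related to baseline through regression to the mean. If leaving depends on baseline in one arm and not in the other, the completers start from different levels, and the difference in mean change picks that up even with no treatment effect. Reasons for leaving could well differ here: one arm is asked to attend 14 group sessions over 7 weeks, while the other waits in usual care. The result could then describe those who stayed and still be reported as intention-to-treat.

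**Working it through.** **Plan's own figures.** The inputs are f = 0.25, 5% significance, 80% power, two groups and two time points (Study Sample). The correlation between time points is not given; 0.5 is assumed. For the between-factors test, λ = f² × N × m / (1 + (m − 1)ρ), with 1 and N − 2 degrees of freedom.
- N = 98: λ = 0.0625 × 98 × 2 / 1.5 = 8.17, power 80.8%.
- N = 96: power 79.9%. The plan's 98 is therefore reproduced.
- 98 × 1.30 = 127.4, rounded up to the plan's 128.

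**Who has both scores.**
- 30% attrition: 128 × 0.70 = 89.6, about 90 analysed and 38 not.
- 13% attrition: 128 × 0.87 = 111.4, about 111 analysed and 17 not.

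**Bias when dropout depends on baseline in the intervention arm only.** Assumptions, none given in the documents: baseline is standard normal with higher meaning better; the pre-post correlation is r; SDs are equal at the two times; there is no treatment effect; control dropout is random; the log-odds of staying in the intervention arm rise by b per SD of baseline. Expected change given baseline x is −(1 − r)x, so

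bias = −(1 − r) × μ,

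where μ is the mean baseline of intervention-arm completers, found by numerical integration.

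| Attrition | b | μ (SD) | r = 0.3 | r = 0.5 | r = 0.7 |
|---|---|---|---|---|---|
| 30% | 0.5 | 0.143 | −0.100 | −0.071 | −0.043 |
| 30% | 1.0 | 0.253 | −0.177 | −0.126 | −0.076 |
| 13% | 0.5 | 0.063 | −0.044 | −0.032 | −0.019 |
| 13% | 1.0 | 0.116 | −0.081 | −0.058 | −0.035 |

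The ranges are about 0.04 to 0.18 SD at 30% and 0.02 to 0.08 SD at 13%. Negative means against CST-HK; the sign reverses if participants with better baselines leave. With the same mechanism in both arms, μ is equal in each and the bias cancels. Simulation at 30% and r = 0.5 gave −0.073 and −0.128 SD for the change score, and about 0 after baseline adjustment.

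As a yardstick, f = 0.25 with two equal groups is 2 × 0.25 = 0.5 SD. A bias of 0.04 to 0.18 SD is 8% to 36% of that.

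**Precision.** The change-score variance is 2(1 − r). The residual variance after baseline adjustment is 1 − r². Their ratio is (1 + r)/2: 0.65 at r = 0.3, 0.75 at r = 0.5 and 0.85 at r = 0.7.

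**Dropout related to the unseen outcome.** If intervention-arm dropouts would have scored g SD worse than completers, beyond what baseline explains, and control dropout is random, then bias = attrition × g in favour of CST-HK. With g = 0.5 (assumed), this is 0.30 × 0.5 = 0.15 SD, or 0.13 × 0.5 = 0.065 SD at the pilot's rate. Baseline adjustment leaves this bias in place.

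**The case against.** The strongest reply is that the plan already contains the remedy for the baseline-driven bias. The ANCOVA adjusts for baseline on both outcomes and gives about zero bias in the same scenario. That stands. What remains is the order: the ANCOVA is a further analysis, and the unadjusted change ANOVA leads.

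A reader might infer that the method contradicts the intention-to-treat statement, or that the plan excludes everyone without a 7-week score. The documents do not support either reading. They never say that such participants are excluded; they are silent, and an unstated imputation is possible. Intention-to-treat also means analysis in the arm allocated, and nothing in the plan departs from that. Exclusion is what the named method does by default.

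A reader might also infer that the result is bound to be biased towards CST-HK. That does not follow. Bias is zero if dropout is unrelated to outcome or acts equally in both arms, and the two mechanisms above can pull in opposite directions. The slopes, the correlation and g are all assumed, and 30% is a planning allowance set against 13% in the pilot.

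Finally, with one follow-up, a mixed model that includes non-completers through their baseline scores gains little over the ANCOVA. That also stands, so the fix does not depend on it.

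**Conclusion.** The point holds as a choice of lead analysis and a gap in missing-data handling. As written, the primary comparison uses by default about 90 of 128 participants at 30% attrition, or about 111 at 13%. It also rests on the less robust and less precise of the two methods that the plan names. Under baseline-dependent dropout in one arm, the bias is about 0.04 to 0.18 SD at 30% attrition and 0.02 to 0.08 SD at 13%, against CST-HK when those with poorer baselines leave the intervention arm. Baseline adjustment removes it, given a linear relation between baseline and outcome that is common to both arms. Neither method protects against dropout related to the unseen outcome, and no planned sensitivity analysis examines it. These sizes are illustrations under stated assumptions, not predictions. The change should be made, but the trial does not fail without it.

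**What to change.** 1. Make the baseline-adjusted analysis primary for both outcomes, with participants in the arm allocated: an ANCOVA of the 7-week score on arm and baseline score, or the equivalent mixed model with a common baseline mean. Demote the change-score ANOVA to secondary.
2. Say how missing 7-week scores are handled and under what assumption.
3. Add one sensitivity analysis: multiple imputation by arm, with missing intervention-arm scores shifted by a delta, for example 0 to 0.5 SD worse.
4. Report the number of missing scores, and baseline scores by completion status, for each arm.

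The cost is a paragraph in the plan and a little more analysis work. No extra participants or measurements are needed. Results may look slightly less favourable under the delta shift. Seeking 7-week interviews from people who stop attending would reduce the problem at source, but that is field work with its own cost, and the steps above do not depend on it. Allowing for randomisation in groups of eight is a separate matter that applies to whichever model is primary.

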- Be able to communicate and understand Cantonese;
- Be able to hear and see well enough to participate in the cognitive stimulation activities;
- No major illness that would affect participation (including clinically significant depressive symptoms or acute psychotic disorders);
- No behavioural problems (e.g., aggression, inappropriate sexual behaviors) or psychotic symptoms (e.g., hallucination, delusion) that would interfere with participation in the intervention;
- A caregiver who is able to give joint informed consent.

Intervention and Procedures

A briefing session will be provided to participants and their family caregivers by the staff of Hong Kong Young Women's Christian Association for recruitment. Upon giving written consent, participants will be randomized into intervention group (n=64) or waitlist control group (n=64) in groups of eight. Two randomization lists will be generated by HKU researchers, one each for residential care units and community care units. Hong Kong Young Women's Christian Association will be informed about the group allocation upon successful recruitment of eight eligible participants. The intervention group will receive the14-session group CST-HK (45 minutes per session, two times a week, for 7 weeks in total) provided by trained facilitators. The wait-list control group will receive usual care in the service units they are attach to and will start their CST-HK programme after an 8-week delay.

A total of 40 CST-HK facilitators without specialized healthcare background will be recruited by Hong Kong Young Women's Christian Association. They are required to attend two 4-hour workshops to acquire the knowledge and skills for delivering CST-HK. The knowledge and skills include the guiding principles, and the theme of each training session. After the workshops, the facilitators will be designated to nine elderly service units mentioned above and practice their learnt knowledge and skills in delivering CST-HK under the supervision of experienced CST-HK interventionists with specialized healthcare background in Hong Kong Young Women's Christian Association. At the end of the practicum, the trainees will be evaluated to ensure the fidelity of CST-HK.

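### Participants are randomised in groups of eight, but neither the main ANOVA nor the sample size allows for clustering

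*Combined protocol and SAP*

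**What the plan says.** Research Design states: "This is a cluster randomized wait-list control study". Under Intervention and Procedures, "participants will be randomized into intervention group (n=64) or waitlist control group (n=64) in groups of eight", and the service provider is "informed about the group allocation upon successful recruitment of eight eligible participants". There are two randomisation lists, one for residential and one for community units. Recruitment is from nine units, two residential and seven community.

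On sample size, Study Sample says: "Repeated measure analysis of variance (ANOVA), between factors will be used". The inputs are given as "Assuming a medium effect size (f = 0.25), 80% power and 5% significance level, with two groups and two time points", from which "a total of 98 participants are required". Then: "We propose a sample size of 128 to accommodate for a 30% attrition rate". No ICC, design effect, number of clusters or correlation between time points is stated.

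On the analysis of quality of life and cognition, Data Analysis says that "ANOVA will be used to assess changes from baseline to 7 weeks after between the intervention group and the wait-list control group". A further ANCOVA adjusts for several covariates, including care setting. Random effects are mentioned only there, in parentheses beside AChEI use. Neither the randomised group nor the service unit is named.

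**The concern.** The unit of randomisation is the group of eight, while the main ANOVA treats the participant as the independent unit. CST-HK is delivered in group sessions, so members of a treated group share facilitators and group dynamics over the same 7 weeks in which change is measured. If their changes are positively correlated as a result, the effective amount of information is smaller than the ANOVA assumes. Its standard errors are then too small on average, and p-values and intervals for both main outcomes overstate the evidence. The 80% power also assumes independent participants.

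Two things limit the problem. Stable differences in level between groups cancel in change scores. Correlation that comes only from care setting does no harm if the two lists balance setting across arms. What matters is the correlation of change within a group beyond setting.

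**Working it through.** **Number of randomised units.** 128 / 8 = 16 groups; 64 / 8 = 8 per arm.

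**Reproducing the 98.** For a between-factors repeated-measures ANOVA with two groups and two time points, the noncentrality is λ = f² × N × 2 / (1 + ρ) on (1, N − 2) df, where ρ is the correlation between time points. With f = 0.25 and 80% power at 5%, the required N is 66, 84, 98, 110 and 122 at ρ = 0, 0.3, 0.5, 0.7 and 0.9. So 98 corresponds to ρ = 0.5, which the documents do not state: λ = 0.0625 × 98 × 2 / 1.5 = 8.17, power 80.8%. It is the figure for independent individuals, with nothing added for clustering.

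**Type I error of the planned ANOVA.** All ICCs of change below are assumed. With n per group and both arms clustered, the variance of the arm difference rises by about 1 + (n − 1) × ICC. For n = 8 this is 1.07, 1.14, 1.35 and 1.70 at ICC 0.01, 0.02, 0.05 and 0.10. The approximate type I error is 2 × [1 − Φ(1.96 / √(design effect))] = 5.8, 6.6, 9.2 and 13.3%. Simulated null trials (8 versus 8 groups, ordinary two-sample test on N − 2 df, 300,000 to 400,000 trials per cell) agree:

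| Scenario | ICC 0.01 | 0.02 | 0.05 | 0.10 |
|---|---|---|---|---|
| Only CST-HK arm clustered, six per group | 5.3% | 5.6% | 6.5% | 8.0% |
| Only CST-HK arm clustered, eight per group | 5.4% | 5.8% | 7.1% | 9.2% |
| Both arms clustered, 30% lost at random (about 90 analysed) | 5.5% | 6.1% | 7.9% | 10.9% |
| Both arms clustered, six per group | 5.5% | 6.2% | 7.9% | 11.0% |
| Both arms clustered, eight per group | 5.8% | 6.6% | 9.2% | 13.4% |
| Half the correlation from balanced care setting, eight per group | – | – | 6.8% | 8.6% |
| All of it from balanced care setting, eight per group | – | – | 4.4% | 3.9% |

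The care-setting rows assume 4 residential and 12 community groups, balanced across arms. At ICC 0 the error is 5.0%. With both arms clustered and eight per group, the ANOVA standard error is too small by about 3, 6, 14 and 24% at the four ICCs.

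A cluster-level test with a stratum term has 16 − 2 − 1 = 13 df. It held 4.9 to 5.1% in the scenarios of the table.

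**Effect on the stated 80%.** Keep the plan's own formula at ρ = 0.5, divide λ by 1 + (N/16 − 1) × ICC, and use the 14 df of a comparison of 16 group means. The ICC here refers to the mean of the two time points, not to change.

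| N analysed | Individual-level df | 14 df, ICC 0 | 0.01 | 0.02 | 0.05 | 0.10 |
|---|---|---|---|---|---|---|
| 128 | 90% | 86% | 83% | 81% | 74% | 65% |
| 98 | 81% | 76% | 74% | 72% | 66% | 58% |
| 90 (128 × 0.7 = 89.6) | 77% | 72% | 70% | 68% | 63% | 56% |

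These rows show only what clustering does to the stated 80%. The between-factors formula tests the average over time points, so they are not the power of the change-score comparison.

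**The case against.** The strongest objection concerns service units. Sixteen groups from nine units means that some units host more than one group, and a unit may hold groups from both arms, so a shared unit effect can partly cancel. In the extreme layout of eight units, each with one group per arm and all correlation at unit level, the planned ANOVA runs at 4.5 and 4.0% at ICC 0.05 and 0.10. A cluster-level test without strata is then very conservative (2.4 and 1.2%). That is correct for that layout, but the plan does not secure it, because randomisation is by setting list and not by unit. With all correlation at unit level, nine units, and groups randomised within setting, the ANOVA still runs at 5.6, 6.5, 8.5 and 12.2% at ICC 0.01, 0.02, 0.05 and 0.10. The stratified 13-df test stays at 4.9 to 5.1%.

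Three further points have some force:

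- Controls receive usual care until after the 7-week assessment, so facilitator and group-session effects act only in the CST-HK arm. The rows with only that arm clustered are therefore the natural ones for this mechanism, and they show less inflation. They still exceed 5% throughout.
- The mixed model is not exactly calibrated when the ICC is near zero. In a balanced simulation without a stratum term, the group variance was estimated as zero in about 40 to 54% of trials at ICC 0 to 0.02. Type I error was about 3.5 to 4.0% if the df then revert to N − 2. That errs on the safe side.
- The power figures do not establish a shortfall for the change-score test. They are not used for that here.

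The wording about random effects does not rescue the plan. Even on a generous reading it belongs to the further ANCOVA, names no cluster and leaves the main ANOVA untouched.

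**Conclusion.** The concern holds and should be corrected before analysis. The mismatch between the unit of randomisation and the main analysis is plain from the text, as is the absence of any allowance for clustering in the sample size. The size of the effect is not known, because the documents give no ICC. Over the assumed range of 0.01 to 0.10, a nominal 5% test has a true error between about 5.3% (ICC 0.01, only the CST-HK arm clustered, six per group) and 13.4% (ICC 0.10, both arms clustered, eight per group). There is no inflation if the ICC of change is zero or if all of the correlation comes from care setting balanced across arms. As written, the ANOVA is valid only under an unstated assumption that the corrected analysis does not need. On the plan's own power formula, the loss of degrees of freedom alone takes 98 analysed participants from 81% to 76%.

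**What to change.** **Data Analysis.** Make the primary analysis of each main outcome a linear mixed model with a random intercept for the randomised group of eight, the care-setting stratum (the two lists) as a fixed effect, and Kenward-Roger or Satterthwaite degrees of freedom. A cluster-level analysis with a stratum term on 13 df would also do; it is simpler, and it is the version whose error rate was checked above. Say explicitly that the random effect is for the randomised group, not AChEI use. Keep a service-unit random effect to a sensitivity analysis at most, since it may be poorly estimable with nine units and 16 groups.

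**Study Sample.** State the assumed correlation between time points and a range of ICCs. Apply the design effect 1 + (n per group − 1) × ICC to the analysis actually planned, and restate the power for 128 enrolled and for the number expected after attrition.

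**Cost.** This is a change of wording in two sections. Intervals will be somewhat wider, degrees of freedom fewer and the stated power less favourable. It restores error control and makes any power shortfall visible, but does not remove one. No extra participants are requested.

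### The main analysis is an unadjusted ANOVA of change; a short ANCOVA on own baseline and care setting should lead, for a modest precision gain that depends on unstated correlations

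*Combined protocol and SAP*

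**What the plan says.** The Data Analysis section assigns the two main outcomes to an unadjusted comparison: "ANOVA will be used to assess changes from baseline to 7 weeks after between the intervention group and the wait-list control group". It then adds a second model: "Further analysis will be conducted by ANCOVA controlling for baseline differences in age, gender, education level, type of care setting", followed by "AChEI use (using random effects) and baseline cognition and quality of life". The baseline scores and care setting appear only in that second model.

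Under Research Design: "This is a cluster randomized wait-list control study". Under Intervention and Procedures: "participants will be randomized into intervention group (n=64) or waitlist control group (n=64) in groups of eight". The same section makes care setting a stratum: "Two randomization lists will be generated by HKU researchers, one each for residential care units and community care units". The Measurements section states its cognition benchmarks as changes, starting with "No deterioration in cognition is defined as a change in the score of" zero or more points. Study Sample gives a requirement of 98 and then says: "We propose a sample size of 128 to accommodate for a 30% attrition rate".

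**The concern.** With two time points, the group-by-time test of a repeated-measures ANOVA is the same as an ANOVA of change. Either reading of the plan therefore gives a lead test that subtracts the whole baseline score. ANCOVA instead lets the data decide how much of it to subtract. Unless the baseline-to-week-7 correlation is close to 1, full subtraction adds noise. The lead test also leaves out the factor on which randomisation was stratified.

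The estimate, interval and p-value that readers take as the main result would then be less precise than the data allow. With only about 16 randomised groups (128/8), precision is scarce, and the variables needed are already collected.

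**Working it through.** **Inputs from the documents.** f = 0.25, 80% power, 5% significance, two groups, two time points, 98 required, 128 recruited, 30% attrition, groups of eight, 64 per arm.

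**Assumptions.** A week-7 difference of 0.5 SD (f = 0.25 with two equal groups is d = 2f); equal variances at both times; rho, the individual baseline-to-week-7 correlation; the ICC; and rc, the correlation of group effects over time. The documents give none of the last three.

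**1. Reproduce 98.** Repeated-measures ANOVA, between factors, with k = 2 time points: noncentrality = f²·N·k / (1 + (k−1)·rho), on 1 and N−2 df. At N = 98 and rho = 0.5 this is 0.0625 × 98 × 2 / 1.5 = 8.17, and power is 0.808; N = 96 gives 0.799. So 98 reproduces at rho of about 0.5. Rho of 0.3, 0.7 and 0.8 would give 84, 110 and 116. The value 0.5 is inferred, not stated. The figure of 128 is 98 × 1.3 = 127.4, rounded up; 30% loss from 128 leaves about 90.

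**2. Variance ratio.** Suppose group effects correlate over time as individual scores do (rc = rho). The variance factor is then 2(1−rho) for change and 1−rho² for ANCOVA, a ratio of (1+rho)/2: 0.75 at rho 0.5, 0.85 at 0.7, 0.90 at 0.8 and 0.95 at 0.9. The difference, (1−rho)², is the change estimate's exposure to chance baseline imbalance. It is the same loss seen another way, not an additional one.

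**3. Cluster-level power.** Average analysed group size n = 90/16 = 5.625. For a group mean:

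- v = ICC + (1−ICC)/n
- c = ICC·rc + (1−ICC)·rho/n
- Var(change) = 2(v−c)
- Var(ANCOVA) = v − c²/v with the best slope, or v(1+rho²) − 2·rho·c with the individual-level slope
- SE² = variance × 4/16; two-sided 5% noncentral t, df 14 (change) or 13 (ANCOVA)

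Worked case, ICC 0.05 and rho = rc = 0.5: v = 0.05 + 0.95/5.625 = 0.2189 and c = 0.1094. Var(change) = 0.2189 and Var(ANCOVA) = 0.1642. The SEs are 0.234 and 0.203, and power is 51.2% and 62.7%.

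| ICC | rho | rc | Change | ANCOVA, best slope | ANCOVA, individual slope |
|---|---|---|---|---|---|
| 0.05 | 0.5 | 0.5 | 51.2% | 62.7% | 62.7% |
| 0.05 | 0.5 | 1.0 | 62.0% | 70.7% | 69.8% |
| 0.10 | 0.5 | 0.5 | 44.7% | 55.4% | 55.4% |
| 0.10 | 0.5 | 0.9 | 59.2% | 66.9% | 65.2% |
| 0.10 | 0.5 | 1.0 | 64.3% | 71.0% | 68.0% |
| 0.05 | 0.7 | 0.7 | 72.8% | 79.0% | 79.0% |
| 0.05 | 0.7 | 1.0 | 83.2% | 87.0% | 86.6% |
| 0.10 | 0.7 | 1.0 | 85.1% | 87.9% | 86.6% |
| 0.05 | 0.8 | 1.0 | 94.7% | 95.9% | 95.7% |
| 0.05 | 0.9 | 0.9 | 99.3% | 99.5% | 99.5% |

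At rho 0.5 the gain runs from 68.0 − 64.3 = 3.7 points to 62.7 − 51.2 = 11.5 points.

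**4. Where the gain stops.** The individual-slope variance equals Var(change) when v(1+rho) = 2c. At rc = 1 this reduces to ICC = (1−ICC)/n, so ICC = 1/(n+1) for any rho. That is 1/9 = 0.11 with full groups of eight and 1/6.625 = 0.15 after 30% loss. With slightly less stable group effects the crossing is somewhat higher: at rc 0.9, rho 0.3 and ICC 0.20, power is 47.8% for change and 47.3% for ANCOVA.

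**5. How the slope is fitted.** If the slope is estimated from the 16 group means instead (6,000 simulated trials, ICC 0.05, rc = rho, df 12), power is 50% against 58% at rho 0.5, and 88% for both at rho 0.8. Fitting to individual scores keeps more of the gain.

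**The case against.** The strongest reply is that nothing is missing. An ANCOVA with both baseline scores and care setting is already planned, the change test is valid, and the plan nowhere says which result will be the headline. That stands and limits the weight of the point: it concerns which of two planned analyses leads. That the ANOVA leads is an inference, though a natural one, since the plan ties it to the main outcomes and calls the ANCOVA further analysis.

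It is also fair to say that the gain could be small. Seven weeks is short, rho could be high, and differencing already removes stable differences in level between settings. No gain from adjusting for care setting has been quantified here. The cognition benchmarks are defined on change, which is a reason to keep reporting change but not to test on it.

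A reader might infer more than the documents support:

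- **That the planned test is biased.** It is not, over randomisations.
- **That about 15 points of power are lost.** That needs rho 0.3 (39% against 55% at ICC 0.05 and rc = rho), and at rho 0.3 the plan's own formula would have given 84, not 98.
- **That any rho up to 0.7 gives a material gain.** At rho 0.7, ICC 0.10 and stable group effects, the individual-slope gain is 1.5 points.
- **That ANCOVA is always more precise.** Step 4 shows where it is not.

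**Conclusion.** The point holds as one of precision. At the correlation of about 0.5 implied by 98, with an assumed ICC of 0.05 to 0.10, 90 analysed in 16 groups and a 0.5 SD difference, a short ANCOVA gains about 4 to 12 power points over the planned change test. With stable group effects the gain falls to a few points or fewer at rho 0.7 to 0.8, and it disappears near 0.9. With highly stable group effects and an ICC above roughly 0.11 to 0.15, an ANCOVA using only the individual-level slope has no advantage.

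The size is therefore uncertain, because the documents state neither rho, the ICC nor the stability of group effects. All the power figures presuppose a term for the randomised group of eight. The main analysis as written names none, and the plan's only mention of random effects is attached to AChEI use. The change is worth making because it is nearly free, not because the planned test fails.

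**What to change.** For each outcome, name as primary a short prespecified ANCOVA of the week-7 score, fitted to individual scores, with that outcome's own baseline and care setting (residential or community) as covariates. Care setting is included because it is the randomisation stratum. Keep the unadjusted change ANOVA and the longer ANCOVA as supportive analyses, and still report the ADAS-Cog change benchmarks.

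The cost is plan wording and about two residual degrees of freedom, one of them at cluster level (14 to 13). No new data are needed. Baseline adjustment does not deal with clustering, so a term for the randomised group of eight must be added to the primary model as a separate correction.

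### The randomised groups of eight have no term in the main ANOVA or the ANCOVA; the only random effect named is on AChEI use

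*Combined protocol and SAP*

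**What the plan says.** Research Design states: "This is a cluster randomized wait-list control study". Under Intervention and Procedures, "participants will be randomized into intervention group (n=64) or waitlist control group (n=64) in groups of eight". The service provider "will be informed about the group allocation upon successful recruitment of eight eligible participants", so each group is complete before its arm is known. There are separate randomisation lists for residential and community units. Study Sample names "nine service units of Hong Kong Young Women's Christian Association, including two residential care units and seven community care units".

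For the main outcomes, Data Analysis says that "ANOVA will be used to assess changes from baseline to 7 weeks after between the intervention group and the wait-list control group". A further ANCOVA adjusts for age, gender, education level, "type of care setting, AChEI use (using random effects) and baseline cognition and quality of life". That bracket is the only mention of random effects in the document.

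The sample size rests on an unclustered test: "Repeated measure analysis of variance (ANOVA), between factors will be used". Its inputs are "Assuming a medium effect size (f = 0.25), 80% power and 5% significance level, with two groups and two time points". No ICC, design effect or cluster term is given anywhere.

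**The concern.** When whole groups are allocated, people in the same group tend to have correlated outcomes. They come from the same service and, in the intervention arm, share the same sessions and facilitators. An analysis that treats all 128 as independent then gives a standard error that is too small and rejects a true null hypothesis more often than 5% of the time.

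The usual remedy is a random effect for the randomised group. The plan has a random effect, but its wording attaches it to AChEI use. That is presumably recorded as yes or no, although the document does not define its levels. A variance component from two levels has one degree of freedom. A reader who sees random effects mentioned in a cluster trial may assume that clustering is covered, when on the text it is not.

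**Working it through.** **Inputs.** From the document: 64 v 64 in groups of eight, so 64/8 = 8 groups per arm and 16 in all; f = 0.25; 98 evaluable and 128 recruited; 30% attrition, which leaves 128 × 0.7 ≈ 90 completers, or 90/16 = 5.6 per group. Assumed, because the document is silent: ICC 0.02 to 0.10, 30% AChEI users, AChEI effects of 0 to 0.5 SD, and a correlation of 0.5 between the two time points.

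**1. The plan's own figure.** For repeated-measures ANOVA, between factors, the noncentrality is λ = f²·N·m/(1+(m−1)ρ) with m = 2 time points. At N = 98 and ρ = 0.5, λ = 0.0625 × 98 × 2/1.5 = 8.17. On 1 and 96 df this gives power 0.808. So 98 is reproduced, with no allowance for clustering.

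**2. Where the random effect sits.** For one two-level random factor, the REML variance is zero when the fixed-effect F is at most 1. Otherwise the fitted contrast is shrunk by the factor 1 − 1/F. The probability of a zero variance, from the noncentral F on 1 and N − 9 df with 30% users, is:

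| AChEI effect (SD) | N = 90 | N = 128 |
|---|---|---|
| 0 | 0.68 | 0.68 |
| 0.2 | 0.52 | 0.46 |
| 0.3 | 0.37 | 0.28 |
| 0.5 | 0.12 | 0.06 |

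A variance can therefore be estimated, but imprecisely: on 1 df its 95% interval runs from about 0.2 to about 1,018 times the estimate.

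**3. Does that matter for the arm comparison?** Hardly. In simulated ANCOVAs with no group term and no true AChEI effect, type I error with AChEI random v fixed was 0.101 v 0.100 at ICC 0.05, and 0.126 v 0.125 at ICC 0.10.

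**4. The missing group term.** The design effect is 1 + (m−1)·ICC, with m now the group size. The naive standard error is 1/√(design effect) of the true one.

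- Full groups of eight: 1 + 7 × 0.02 = 1.14 and 1 + 7 × 0.05 = 1.35. The naive SE is 0.94 and 0.86 of the true SE, so it is 6% and 14% too small.
- 90 completers: 1 + 4.625 × 0.02 = 1.09 and 1 + 4.625 × 0.05 = 1.23. The naive SE is 4% and 10% too small.

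Simulating 16 groups of eight with no treatment effect (200,000 trials per ICC) and comparing the arms without a group term gives type I error 0.066, 0.092 and 0.134 at ICC 0.02, 0.05 and 0.10. Smaller runs at ICC 0.10 gave 0.133 and 0.140. A t test on the group means (14 df) gives 0.050 at each ICC.

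**5. What respecting the group costs.** Interval width is multiplied by √(design effect) × t₁₄/t₁₂₆ = √(design effect) × 2.145/1.979.

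- ICC 0.02: 1.068 × 1.084 = 1.16.
- ICC 0.05: 1.162 × 1.084 = 1.26.

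Power with all 128 analysed, using the plan's f and ρ = 0.5 (a standardised difference of 0.5/√0.75 = 0.577), is 0.81, 0.74 and 0.64 at ICC 0.02, 0.05 and 0.10. Ignoring clustering, the same 128 give 0.90.

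**The case against.** The bracket concerns a nuisance covariate in a secondary analysis. The variance is set to zero only when the AChEI difference is no larger than its own noise, and the arm comparison barely moves. The bracket may also be loose drafting: it could cover the whole covariate list, or signal that a mixed model was intended. Finally, the ICC, the AChEI prevalence and the AChEI effect are all absent from the document, so the size of any harm depends on assumptions.

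Most of this stands. A reader might infer that the AChEI variance cannot be estimated at all, or that the treatment effect would lose its AChEI adjustment in a way that distorts the result. The documents do not support either. REML returns an estimate, how often it is zero depends on an unknown effect, and step 3 shows no material change in type I error.

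The alternative readings do not rescue the plan. If the bracket covers care setting, that too has two levels. If it covers the whole list, the randomised group is not on the list. If a mixed model for clustering was meant, the text does not say which unit is random. The main ANOVA has no such bracket at all, so the omission is not confined to a secondary analysis.

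**Conclusion.** The point holds as an omission of the randomised group from both the main and the adjusted analysis, compounded by a phrase that could hide it. At assumed ICCs of 0.02 to 0.05, type I error is about 0.07 to 0.09 in place of 0.05 with all 128 analysed; at ICC 0.10 it is 0.13 to 0.14. The SE percentages rest on equal groups and on one ICC common to both arms. At an ICC near zero the problem would largely disappear, but the document gives no reason to expect that.

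The placement of the random effect on AChEI use is a wording fault that needs correcting. On its own it is not a threat to the trial's conclusion.

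**What to change.** In Data Analysis:

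- Enter AChEI use and care setting as fixed effects alongside the other covariates. Care setting also defines the two randomisation lists.
- In both the main comparison and the ANCOVA, include a random intercept for the randomised group, with a small-sample degrees-of-freedom correction (for example Kenward-Roger) suited to 16 groups. Consider whether service unit also needs a term.
- Delete the bracket after AChEI use.

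In Study Sample, restate power with a stated ICC or a range of ICCs.

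This is a change of a sentence or two and needs no new data, provided that each participant's group is recorded. The cost is precision: confidence intervals about 16 to 26% wider at ICC 0.02 to 0.05 with full groups of eight, and power below the unclustered figure (0.74 against 0.90 at ICC 0.05 with all 128 analysed, and lower with attrition).
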